## **Data Collection and Processing Techniques and Procedures**

The patients are admitted to the clinic where they receive a medical evaluation in which they are diagnosed as patients with primary PE. Once this occurs, they are invited to participate in the study by their own voluntary choice. If the patient is interested in participating, the informed consent process is conducted and the corresponding document is signed. Then, an informational email is sent to the telephone center staff responsible for investigations, so that the information required from the patient is inputted into the corresponding database for the purpose of following-up on all of the therapy and follow-up appointments.

Prior to receiving therapy, the patient will perform a two-week process in which he will measure the intravaginal latency time with a digital timer or stopwatch APP and record it on the in-home chart. This has two objectives: first, the patient adapts to the way in which he will measure this time when having sexual relations during the study; second, to have a more precise reference point for the initial IELT, which will be used as a baseline to demonstrate changes during the study protocol.

The therapy will be conducted as follows: Three (3) sessions per week for twelve (12) consecutive weeks, with a duration of 30 minutes each, with the application of 20 Hertz with a pulse amplitude of 200 MI sec. in each session. The intensity will be applied individually for each patient depending on the tolerance of the individual. In each session, it is normal to have plantar flexion of the foot and flexion of the first toe, and after the session and particularly during the first sessions there is the possibility of muscle pain, which should be tolerable. Appendices 3 and 4 provide a more detailed description of the scheme and procedure.

During the study, each patient will have an in-home chart which he must fill out after each sexual encounter and bring to each appointment. The patients will be given strict telephone follow-up calls aimed at their keeping their monthly follow-up appointments, or if not possible due to lack of time a virtual appointment will be conducted by the physician using skype or by telephone.

It is essential that each patient who is admitted into the study complies with the scheduled electrostimulation sessions. If one of the protocols is broken, the patient will be treated as a loss to follow-up since his information could be incorrect.

PEDT and IELT measurements will be taken at the beginning of therapy, at the halfway point, upon finishing the protocol and three months after completion.

All of the information will be recorded in the electronic clinical chart that is already in use at the Boston Medical Group. All of the clinical data will be stored in a flat Excel database. Upon completing the collection of the entire sample, the clinical information that is lacking will be extracted from the electronic clinical chart. This information will be exported to a flat file to be read later by a statistical package.

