#### **Exclusion criteria:**

- Diagnosis of erectile dysfunction according to the IIFE 5 (score under 21).
- A PEDT score under 8.
- Use of treatment for premature ejaculation during the study or over the 6 months prior to beginning the study.
- Use of pacemaker or heart defibrillator.
- Epilepsy or convulsions
- Venous insufficiency (varices) or cutaneous wounds or injuries on the lower extremities.
- Congenital or acquired anatomical abnormalities of the penis.
- Taking medications that affect ejaculation control, including psychiatric medications, opioid analgesics and medications for pathologies of the prostate such as alpha blockers.
- Psychological or psychiatric disorders that prevent the patient from undergoing the treatment or recording the measurements as established.
- Difficulty going to the clinic 3 times per week as required by the protocol.
- Patients with precoital premature ejaculation.
- Use of barrier contraceptive methods or local anesthetics.

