#### **Sample size**

The "single stage procedure" proposed by Fleming was used to estimate the sample size for this type of trial. For  $P_0=10\%$  and  $P_1=30\%$  with an alpha error of 5% and a beta of 80%, 18 patients need to be included in order to prove the study's hypothesis. After adjusting this number by a percentage of loss of 30%, which is observed in daily practice, 24 patients will be included in the study.

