## OUTCOMES

### Primary Outcome

Proportion of patients with clinical improvement of premature ejaculation, defined as a tripling of the baseline time (without treatment), as measured by the IELT (intravaginal ejaculation latency time) during the therapy and three months after completion.

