## OUTCOME VARIABLES

Since the aim is to evaluate possible changes in the length of time of the appearance of the ejaculatory reflex, two tools will be used to quantify this datum: the PDET and IELT (Appendix 1). The first is a questionnaire that evaluates the perception the patient has of his situation, and the second will be measured with a timer which the patient will use to document the time it takes between vaginal penetration and the appearance of ejaculation, data which must be recorded on the in-home chart (Appendix 2) which each patient will have and which he must bring to each follow-up appointment. These data will be used to quantify the following variables:

- IELT and PEDT at week 6 of the protocol (halfway point).
- IELT and PEDT at the end of treatment.
- IELT and PEDT three months after finishing the protocol.

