### Data Analysis Plan

A descriptive analysis will be performed of the sociodemographic and clinical characteristics of the research subjects. For the categorical variables, absolute and relative frequencies will be estimated. For the numerical variables, central tendency and dispersion measurements will be estimated.

To evaluate the efficacy of this new therapy, the proportion of patients whose illness improves will be estimated and compared with the expected proportion proposed by the hypothesis (30%). Improvement is defined as the tripling of the baseline (without treatment) intravaginal latency time.

The safety will be evaluated by estimating the incidence of adverse events experienced by the patients during the study. These will be classified by the degree of severity according to WHO criteria.

The analyses will be performed with Stata 14.

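### A broken protocol turns a patient into a loss to follow-up and no denominator is stated, so the response rate may describe compliers only

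*Combined protocol and SAP*

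**What the plan says.** The rule is in Data Collection and Processing Techniques and Procedures. The paragraph opens with attendance: "It is essential that each patient who is admitted into the study complies with the scheduled electrostimulation sessions". It ends: "If one of the protocols is broken, the patient will be treated as a loss to follow-up since his information could be incorrect". Three sessions a week for twelve weeks makes 36 sessions. The text gives no tolerance for missed sessions and does not define a break. Appendices 3 and 4, described there as covering the scheme and procedure of the therapy, were not available for this review.

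The intravaginal ejaculation latency time (IELT) is timed at home: "each patient will have an in-home chart which he must fill out after each sexual encounter". The primary outcome is the proportion of patients whose IELT triples from baseline, "during the therapy and three months after completion". Data Analysis Plan estimates that proportion and compares it with 30%. It names no analysis set, no rule for missing IELT, no test and no cut-off. Sample size uses P0 = 10% and P1 = 30%, finds 18 patients, and raises this to 24 for a 30% loss.

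**The concern.** A missed session does not make a stopwatch reading wrong. Read as an attendance rule, the sentence can set aside IELT data that exist and are usable, because of something the patient did after treatment began. Men who notice no benefit may be the ones who stop attending. There is no control arm in which the same selection would occur and partly cancel, because the result is set against a fixed proportion.

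The plan does not say what being treated as a loss means for the analysis. If losses count as failures, there is no upward bias. If they leave the denominator, the rate describes compliers and may overstate the response among all treated men. Two things in the plan point to the second reading: the stated reason, which implies that the man's data will not be used, and a sample size raised so that enough patients remain after losses. Neither is a statement of the analysis set.

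**Working it through.** **Inputs from Sample size:** P0 = 10%, P1 = 30%, alpha 5%, 18 patients, 30% loss, 24 enrolled. The stated beta of 80% is read as power.

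**The plan's own figures.** One-sided normal approximation: n = [(1.645·√(0.1·0.9) + 0.842·√(0.3·0.7)) / 0.2]² = 19.3, so 20, within two of the stated 18. Then 18 × 1.3 = 23.4, so 24, as stated. With 30% lost, 24 × 0.7 = 16.8, so about 17 men remain.

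**Assumptions, not in the plan.** Losses leave the denominator; the test is one-sided against 10%; the cut-off is the smallest count with risk of 5% or less, which is 5 of 17. Let p be the response rate in all treated men and r the response of removed men relative to compliers. The documents give no value for r, so a range is shown.

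**Formulas.** Complier rate c = p / (0.7 + 0.3r). Inflation = c / p. Risk of success for completers = P(Bin(17, c) ≥ 5).

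At p = 10%:

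| r | c | Inflation | Risk, completers, 5 of 17 | Risk, all 24, no IELT = failure, cut-off 6 |
|---|---|---|---|---|
| 1 (no selection) | 10.0% | 1.00 | 2.2% | 0.5% |
| 0.5 | 11.8% | 1.18 | 4.1% | 1.1% |
| 0.25 | 12.9% | 1.29 | 5.8% | 1.8% |
| 0 (none respond) | 14.3% | 1.43 | 8.4% | 2.8% |

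The last column is P(Bin(24, 0.7c) ≥ 6), with no IELT from any of the removed men.

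**Sensitivity.** With 17 analysed and a cut-off of 5, the risk passes 5% when r falls below about 0.36. That threshold belongs to this case only. At 20% loss (19 analysed, cut-off 5) the risks for r = 1, 0.5 and 0 are 3.5%, 5.2% and 7.9%. At 10% loss (22 analysed, cut-off 6) they are 1.8%, 2.3% and 2.9%.

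**Power at p = 30%.** For r = 1, 0.5 and 0, completers at 5 of 17 have 61%, 77% and 92%; the last two partly reflect the inflated complier rate. All 24 at a cut-off of 6, with 30% lacking IELT counted as failures, have 39%, 56% and 77%. If IELT is obtained from every non-complier, power is 77% whatever r is.

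**The case against.** **Exclusion is inferred.** This stands. Raising a sample size for loss is routine and does not define an analysis set. The firm finding is that the plan has a rule creating losses and no rule for counting them.

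**The denominator decides the conclusion.** A reader might infer this from five responders, all compliers: 5/24 = 20.8% (one-sided p = 0.085 against 10%) but 5/17 = 29.4% (p = 0.022). The documents do not support that as a statement about the written analysis. Data Analysis Plan names 30% as comparator. Both rates lie below 30% and neither differs clearly from it (exact lower tails 0.23 and 0.60). The reversal needs a one-sided test against 10%, which the plan uses for sample size but does not state as its analysis, and five is the count that falls between the two cut-offs.

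**Compliers may be the target.** Response under the full schedule is a legitimate question in an uncontrolled phase II study, and men who received less stimulation may respond less for that reason. The complier rate is then not wrong, but it answers a different question. The terms bias and false success apply only if the target is all treated men, and the plan does not say which it wants.

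**Some breaks do affect IELT.** The wording may reach beyond attendance, to poor chart keeping or to a listed exclusion: "Use of treatment for premature ejaculation during the study or over the 6 months prior to beginning the study". For those, doubting the data is reasonable. This supports separate rules for missed sessions and for other breaks.

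**Conclusion.** The point holds in a limited form. The plan converts protocol breaks into losses, gives a reason that does not fit missed sessions, and states no denominator. If losses are dropped and the target is all treated men, the response rate is inflated by a factor between 1 and 1.43 at the planned 30% loss. The risk of a wrong success against 10% then lies between 2.2% and 8.4%. It stays under 5% at half response in the 30%-loss case, and under 3% throughout at 10% loss. The size rests on the assumed test, the cut-off and the response among removed men, for which the documents give no data. It would be too strong to say that the plan excludes non-compliers or that its result will be biased. This is a cheap improvement, not a fatal flaw.

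**What to change.** Replace the last sentence of that paragraph with wording such as:

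> All patients who receive at least one session form the denominator of the primary response rate. Missed sessions do not remove a patient; his IELT continues to be collected and is analysed as measured. A patient with no IELT at the time point analysed, or who has by then used another premature ejaculation treatment, counts as a non-responder. An analysis of patients who followed the full schedule is supportive only.

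If a success cut-off against 10% is used, set it for the number actually in the denominator. Consent and two weeks of home timing come before therapy, so fewer than 24 may start. The smallest count with one-sided risk of 5% or less is 6 for 21 to 24 patients (2.8% at 24) and 5 for 17 to 20 (4.3% at 20).

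The cost is wording, plus continued collection of charts already issued, through the calls and virtual appointments already planned. The drawback is a lower reported rate, biased downward if men without IELT would have responded, and less power. With 30% lacking IELT, a true rate of 30% and 24 in the denominator, power is 39% with no selection, against 61% for completers at 5 of 17. Obtaining IELT from half of the non-compliers raises the 39% to 60%, and obtaining it from all raises it to 77%. Full recovery may be hard to achieve, so follow-up of men who miss sessions matters as much as the denominator.

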## **EXPECTED IMPACT**

By determining the efficacy and safety of TPTNS (transcutaneous posterior tibial nerve stimulation) for treating premature ejaculation, it will be possible to conduct a comparative evaluation and thereafter implement new therapies to treat this condition, benefiting patients by having different treatment options to offer.

In terms of generating knowledge, two presentations are planned at national and/or international urology conferences or conferences related to the treatment of male sexual pathology. At least one article presenting information about the results from the study will be published in an international indexed journal.

## **ETHICAL ASPECTS**

The research will comply with the legal and ethical guidelines described by 1993 Resolution No. 8430 established by the Colombia Ministry of Health and other national regulations. The principles developed by the World Medical Association for research involving human subjects, as stated in the Declaration of Helsinki, will be respected and complied with as will the ethical guidelines by the Council for International Organizations of Medical Sciences (CIOMS) and the Belmont Report.

The intervention to be evaluated has been proven to be effective for other conditions having a similar physiopathology, and the published reports of scientific evidence show that the rate of adverse events is very near zero or zero. The intervention will be administered by personnel who have all of the technical skills and experience required to administer the intervention as well as to treat possible adverse events.

According to Article 11 of The Ministry of Health's 1993 Resolution No. 8430, the risk associated with the present research is considered to be higher than the minimum. In compliance with this legislation, approval will be requested from the Ethics Committee for the authorization of the development of this investigation.

Each subject will be informed of all of the possible consequences from participating in this investigation (regardless of their probability of occurrence). Informed consent will be explained and obtained, and the individual will be entirely free to decline to participate in the study without this decision having any affect on the medical care for his illness.

In addition, to address the need to protect the privacy of each research subject and his partner an instructional guide will be made available for the confidential handling of the information collected. The confidentiality of the subjects will be ensured and, therefore, the databases will be housed in the Boston Medical Group's offices and only the study's researchers will have access to them.

Lastly, the study will ensure that the researchers possess the technical competency required for conducting this study and that they have the tools needed to manage and use the research data.

